2. OBJECTIVES AND ENDPOINTS

2.1. Objectives

The primary objective of this study is:

- To evaluate the efficacy of GS-9973 in subjects with relapsed or refractory hematologic malignancies

The secondary objectives of this study are:

- To evaluate the safety and tolerability of GS-9973 in subjects with relapsed or refractory hematologic malignancies
- To evaluate GS-9973 exposures in subjects with relapsed or refractory hematologic malignancies

2.2. Endpoints

Primary Endpoints

- PFS rate at 16 weeks (CLL after BCR targeted therapy, MCL and DLBCL) or 24 weeks (CLL and iNHL) as established for each malignancy. PFS is defined as the interval from the first dose of GS-9973 to the earlier of the first documentation of definitive disease progression or death from any cause. The findings of the IRC will be considered primary for analyses of PFS rate.

Secondary Endpoints:

- Safety: abnormal laboratory data, adverse events (AEs) and treatment-emergent AEs. Safety will be assessed by grading of laboratory values and AEs according to the NCI Common Terminology Criteria for Adverse Events (CTCAE) version 4.03.

Efficacy:

- Objective response rate (ORR). ORR will be determined from the subjects' best response during GS-9973 therapy and will include complete response (CR) or partial response (PR) [or very good partial response (VGPR) or minor response (MR) for subjects with LPL/WM].
- Duration of response (DOR). DOR will be defined as time from the first response (CR or PR [or VGPR or MR for subjects with LPL/WM]) is achieved until the earlier of the first documentation of definitive disease progression or death from any cause.
- Time to response (TTR). TTR will be defined as time from the first dose of GS-9973 to the first time the response (CR or PR [or VGPR or MR for subjects with LPL/WM]) is achieved.

The findings of the IRC will be considered primary for analyses of secondary efficacy endpoints.

Exploratory Endpoints:

[figure not shown]
- [REDACTED]
- [REDACTED]

3. STUDY DESIGN

3.1. Overview

This protocol describes a Phase 2, open-label study evaluating the efficacy, safety, tolerability, pharmacokinetics and pharmacodynamics of GS-9973/GS-9973 SDD in subjects with relapsed or refractory hematologic malignancies. Eight separate cohorts consisting of subjects with CLL, iNHL, MCL, or DLBCL will be studied concurrently. Subjects with iNHL will be studied in 2 cohorts: 1 consisting of only subjects with FL and the other consisting of subjects with LPL/WM, SLL, and MZL. Two additional cohorts have been added to the study under amendment 4, consisting of subjects with CLL who have previously been treated with ibrutinib or idelalisib and now have progressive disease (CLL prior BTK inhibitor exposure and CLL prior PI3K inhibitor exposure, respectively). A dose ranging cohort consists of 100 mg, 200 mg and 400 mg (200 mg x 2) new formulation of GS-9973 SDD are added under amendment 5. (See [Figure 3-1](#)). As of protocol amendment 8, subjects receiving GS-9973 MM formulation will be transitioned to the GS-9973 SDD formulation (Section [5.3.5](#)).

Figure 3-1. Study Schema

3.1.1. CLL, FL, DLBCL, MCL

A Bayesian, continuous data review approach will be used to update the estimates of PFS rates at 16 weeks (CLL after BCR targeted therapy, MCL and DLBCL) or 24 weeks (CLL and iNHL) as each subject's primary endpoint becomes available for a malignancy. The criterion used for the futility boundary is defined as highly likely (>90%) that the PFS rates at 16 weeks (CLL after BCR targeted therapy, MCL and DLBCL) or 24 weeks (CLL and iNHL) are less than 0.2 given the available subjects' efficacy data.

Futility assessment begins when the first 10 subjects' primary endpoints become available. Thereafter, continuous data review will be conducted when a new primary endpoint becomes available.

- If the futility criterion is not met, subsequent subjects will be enrolled until a total of pre-defined number of subjects are recruited for a cohort.
- If the futility criterion is met, the sponsor will consider terminating enrollment to that malignancy, taking into account efficacy, drug exposure and subtype (for DLBCL), unless there are subjects who remain on treatment and have not yet reached 16 weeks (CLL after BCR targeted therapy, MCL and DLBCL) or 24 weeks (CLL and FL). In this case, enrollment will be suspended until the next on-going subjects' primary endpoint becomes available, and another data review is conducted. If, after review of all available subjects, the futility boundary has still been crossed and the lack of drug exposure or for DLBCL, subtype does not explain the lack of activity, enrollment to that malignancy will be terminated.

The futility boundary is provided in [Figure 3-2](#) with details in Section 8.6. The boundary is represented in terms of the total number of subjects and the number of progression-free subjects at Week 16 (CLL after BCR targeted therapy, MCL and DLBCL) or Week 24 (CLL and FL). Subjects who withdraw or are lost to follow-up before Week 16 (CLL after BCR targeted therapy, MCL and DLBCL) or week 24 (CLL and FL) will be considered as not achieving PFS for the analysis.

At each data review, if the observed ratio of the number of PFS at Week 16 (CLL after BCR targeted therapy, MCL and DLBCL) or Week 24 (CLL and FL) over the total number of subjects is at or below the futility boundary, then the futility criterion has been met.

The data review for the CLL prior BTK inhibitor exposure and CLL prior PI3K inhibitor exposure cohorts will be conducted independently for Richter's and non-Richter's.

3.1.2. CLL Dose Ranging Cohort

[figure not shown]
For the CLL dose ranging cohort, subjects enrolled will be randomized 1:1:1 to receive 100 mg, 200 mg or 400 mg (200 mg x 2) of GS-9973 SDD BID. Therefore 20 subjects are treated at each of the three dose levels.

Because the CLL dose ranging cohort consists of 3 different dose levels each with approximately 20 subjects, the continuation data review of futility will not be conducted for this cohort.

3.1.3. LPL, SLL, MZL

Because the ‘other non-FL iNHL’ cohort consists of 3 different histologies, accrual will continue to a maximum of 45 subjects without a Bayesian analysis.

Figure 3-2. Futility Boundary with Prior Distribution Beta (0.5, 1.5)

3.2. Treatment Regimen

Initially subjects with iNHL and NHL will receive treatment with 800 mg GS-9973 BID (under fasted conditions (as defined in Section 5.5.10)). As of protocol amendment 8, subjects receiving GS-9973 MM formulation will be transitioned to the GS-9973 SDD formulation (Section 5.3.5).

GS-9973 SDD doses of 100, 200 or 400 mg given BID will be studied in the additional cohorts. A specific dosing regimen will be selected based upon the emerging pharmacodynamic, pharmacokinetic and anti-tumor data from the CLL dose ranging subjects and all cohorts will be transition to the dose level of GS-9973 SDD.

Initially subjects in the CLL prior BTK inhibitor exposure or CLL prior PI3K inhibitor exposure cohorts will receive GS-9973 SDD 400 mg twice daily (BID). Subjects in the CLL dose ranging cohorts will receive the GS-9973 SDD at the dose level assigned in the randomization.

For study purposes, a cycle is considered to be 28 days. In the absence of toxicity requiring a drug holiday (as defined in Section 8.10), dosing will be continuous without interruption. Subjects will have evaluations for safety and provide blood for drug levels and pharmacodynamic monitoring prior to starting treatment and then 1.5 hours thereafter per the following schedule: at initial dose, weekly during Cycle 1, every 2 weeks during Cycle 2, and then once each cycle thereafter. Additional PK samples will be collected at 4 hours after dosing on Cycle 1 Day 1 and Cycle 1 Day 8. Subjects will undergo a radiographic assessment to determine their tumor response to treatment every 8 weeks during the first 24 weeks and then every 12 weeks thereafter for all diagnoses, except LPL/WM who did not have measurable disease at the time of the study and who are not suspected to have measurable disease at the time of progression. For those LPL/WM patients, the reassessments will consist of bone marrow evaluation, serum monoclonal IgM, done by same technique as used in screening, and cryoglobulin. A bone marrow must be done at PD if that is the only source of the PD and at CR to confirm the CR to determine their tumor response to treatment every 8 weeks during the first 24 weeks and then every 12 weeks thereafter.

Treatment with GS-9973 or GS-9973 SDD may continue in the absence of disease progression or unacceptable toxicity.

4. SUBJECT POPULATION

4.1. Number of Subjects and Subject Selection

Subjects with one of the designated malignancies who meet the eligibility criteria will be studied. Up to 60 subjects for the CLL dose ranging cohort and CLL BCR targeted therapy cohorts (CLL prior BTK inhibitor exposure and CLL prior PI3K inhibitor exposure, respectively), up to 40 subjects for each of the other cohorts and up to 8 cohorts (385 subjects in total) will be studied.

Subjects with a documented diagnosis of histologically or cytologically confirmed CLL and selected types of B-cell NHL, with progressive disease are eligible for the study:

- CLL as established by the International Workshop on CLL (IWCLL) {[Hallek 2008](#)}. Subjects with atypical immunophenotype must lack t(11;14) translocation or cyclin D1 over-expression.
- B-cell NHL of the following subtypes as defined by the World Health Organization (WHO) Lymphoma Classification:
 - MCL
 - DLBCL
 - iNHL

4.2. Eligibility Criteria

4.2.1. Inclusion Criteria

Subjects must meet all of the following inclusion criteria to be eligible for participation in this study:

- 1) Male or female \geq 18 years of age
 - a) Diagnosis of B-cell iNHL, DLBCL, MCL (mantle cell, nodal, diffuse or blastoid), or CLL as documented by medical records and with histology based on criteria established by the World Health Organization. If the subject has DLBCL, subtyping is required. Submission of 15 unstained slides is required for subtyping if the subtype is not already known. Subjects for whom tissue is not available but the subtype is already known may be included if pathology report including the subtype is provided.
 - b) If the subject has iNHL, the lymph node histology report confirms 1 of the following subtypes:
 - i) FL Grade 1, 2, or 3a

- ii) SLL (ie, SLL/CLL histology with an absolute lymphocyte count of $< 5 \times 10^9/L$ at diagnosis and on Screening laboratory assessment performed within 35 days prior to the start of study drug administration)
- iii) LPL/WM
- iv) MZL (splenic, nodal, or extranodal)

2) **For institutions that have Phase 3 or Phase 4 protocols studying idelalisib (Zydelig):** subjects with malignancies being studied in these protocols must be a screen failure in the respective idelalisib protocol

3) Prior treatment for lymphoid malignancy and requiring treatment for progressive disease. Criteria for progressive disease is established Cheson criteria for NHL and by IWCLL criteria for CLL

- a) LPL/WM patients do not need to have progressive disease but need to meet criteria of needing treatment per Update on Recommendations for Assessing Response from the Third International Workshop on Waldenström's Macroglobulinemia

4) (see Section 4 for details)

- a) Subjects with de novo DLBCL for whom there is no curative option with conventional treatment
- b) If the subject has MCL, iNHL, or BCR based therapy naïve CLL, the prior treatment must be comprised of at least 1 of the following:
 - i) regimen containing a therapeutic antibody administered for ≥ 2 doses of antibody treatment
 - ii) regimen containing ≥ 1 cytotoxic agent administered for ≥ 2 cycles of cytotoxic treatment
 - iii) regimen containing yttrium⁹⁰-ibritumomab tiuxetan or iodine¹³¹-tositumomab
 - iv) experimental therapy as part of clinical trial protocol
- c) The previously BCR treated patients will be limited to subjects with CLL (other BCR targeted therapies may be accepted after approval of the medical monitor) only in the context of this cohort are Richter's transformation eligible.
 - i) CLL subjects whom have had more than 1 BCR targeted therapy will be enrolled into the cohort of the most recent treatment ibrutinib or idelalisib received prior to progression.

- 5) Presence of radiographically measurable progressive disease as defined using Cheson criteria for NHL, and iNHL and by IWCLL criteria for CLL; lymphadenopathy or extranodal lymphoid malignancy (defined as the presence of ≥ 1 lesion that measures ≥ 2.0 cm in the longest diameter [LD] and ≥ 1.0 cm in the longest perpendicular diameter [LPD] as assessed by CT or MRI);
 - a) Subjects with LPL/WM who do not have radiographically measurable progressive disease must have a monoclonal serum IgM $\geq 2x$ ULN as verified by serum protein electrophoresis (SPEP) and with lymphoplasmacytic marrow involvement are eligible. LPL/WM enrollment is limited to those sites which have cryoglobulin analysis capabilities
- 6) All acute toxic effects of any prior antitumor therapy resolved to Grade ≤ 1 before the start of study drug (with the exception of alopecia [Grade 1 or 2 permitted], neurotoxicity [Grade 1 or 2 permitted], or bone marrow parameters [Grade 1, 2, or 3 permitted])
- 7) Karnofsky performance status of ≥ 60
- 8) Life expectancy of at least 3 months
- 9) Required screening laboratory data (within 5 weeks prior to administration of study drug) as shown in **Table 4-1**. *Note: Confirmation should be considered for out-of-range values to determine if the abnormality is real or artifactual. Values used for screening must be obtained within the screening period and should be the most recent measurement obtained. Subjects with any degree of neutropenia, thrombocytopenia, or anemia with documentation that it is due to malignancy may enroll.*

Table 4-1. Required Screening Laboratory Values

Organ System	Parameter	Required Value
Hematopoietic	ANC	$\geq 0.5 \times 10^9/L$
	Platelets	$\geq 50 \times 10^9/L$
	Hemoglobin	$\geq 80 \text{ g/L (8.0 g/dL)}$
Hepatic	Serum total bilirubin	$\leq 1.5 \times \text{ULN}$ (unless elevated due to Gilbert's syndrome or hemolysis)
	Serum ALT	$\leq 2.5 \times \text{ULN}$
	Serum AST	
Renal	Serum creatinine OR Estimated creatinine clearance	$< 1.5 \times \text{ULN}$ OR $\geq 60 \text{ ml/min}$ as calculated by the Cockcroft-Gault method
Coagulation	INR ^a	< 1.7
Pregnancy	β -HCG ^b	Negative
Infection	HIV	Negative HIV antibody
	HBV	Negative HBsAg and negative HBc antibody
	HCV	Negative viral RNA (if HCV antibody is positive)

^a For subjects on anticoagulative therapy the required value is < 3.0

^b For women of childbearing potential only; serum β -HCG must be negative during screening and serum β -HCG or urine dipstick pregnancy test must be negative at start of study therapy

- 10) For female subjects of childbearing potential, willingness to abstain from heterosexual intercourse or use a protocol-recommended method of contraception from the screening visit throughout the study treatment period and for 30 days following the last dose of GS-9973. *See Section 7.11 for information regarding recommendations for contraception*
- 11) For male subjects of childbearing potential having intercourse with females of childbearing potential, willingness to abstain from heterosexual intercourse or use a protocol-recommended method of contraception from the start of study drug throughout the study treatment period and for 90 days following the last dose of GS-9973 or GS-9973 SDD and to refrain from sperm donation from the start of study drug throughout the study treatment period and for 90 days following the last dose of GS-9973 or GS-9973 SDD. *See Section 7.11 for information regarding recommendations for contraception*
- 12) Willingness to comply with scheduled visits, drug administration plan, imaging studies, laboratory tests, other study procedures, and study restrictions
- 13) Have the ability to understand and sign a written informed consent form, which must be obtained prior to initiation of any study specific procedures

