- 3) Prior treatment for lymphoid malignancy and requiring treatment for progressive disease. Criteria for progressive disease is established Cheson criteria for NHL and by IWCLL criteria for CLL, and for LPL/WM patients per Update on Recommendations for Assessing Response from the Third International Workshop on Waldenström's Macroglobulinemia
- 4) (see Section 4 for details)
 - a) Subjects with de novo DLBCL for whom there is no curative option with conventional treatment
 - b) If the subject has MCL, iNHL, or BCR based therapy naïve CLL, the prior treatment must be comprised of at least 1 of the following:
 - i) regimen containing a therapeutic antibody administered for ≥ 2 doses of antibody treatment
 - ii) regimen containing ≥ 1 cytotoxic agent administered for ≥ 2 cycles of cytotoxic treatment

- iii) regimen containing yttrium⁹⁰-ibritumomab tiuxetan or iodine¹³¹-tositumomab
- iv) experimental therapy as part of a clinical trial protocol
- c) The previously BCR treated patients will be limited to subjects with CLL (other BCR targeted therapies may be accepted after approval of the medical monitor) only in the context of this cohort are Richter's transformation eligible.
 - i) CLL subjects whom have had more than 1 BCR targeted therapy will be enrolled into the cohort of the most recent treatment ibrutinib or idelalisib received prior to progression.
- 5) Presence of radiographically measurable progressive disease as defined using Cheson criteria for NHL, and iNHL and by IWCLL criteria for CLL; lymphadenopathy or extranodal lymphoid malignancy (defined as the presence of ≥ 1 lesion that measures ≥ 2.0 cm in the longest diameter [LD] and ≥ 1.0 cm in the longest perpendicular diameter [LPD] as assessed by CT or MRI);
 - a) Subjects with LPL/WM who do not have radiographically measurable progressive disease must have a monoclonal serum IgM $\geq 2x$ ULN, as verified by serum protein electrophoresis (SPEP) and with lymphoplasmacytic marrow involvement are eligible. LPL/WM enrollment is limited to those sites which have cryoglobulin analysis capabilities
- 6) All acute toxic effects of any prior antitumor therapy resolved to Grade ≤ 1 before the start of study drug (with the exception of alopecia [Grade 1 or 2 permitted], neurotoxicity [Grade 1 or 2 permitted], or bone marrow parameters [Grade 1, 2, or 3 permitted])
- 7) Karnofsky performance status of ≥ 60
- 8) Life expectancy of at least 3 months

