### 3.4. Examination of Subject Subsets

No planned subset analyses.

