## **6. EFFICACY ANALYSES**

### **6.1. Primary Efficacy Endpoint**

#### **6.1.1. Definition of the Primary Efficacy Endpoint**

The primary efficacy endpoint of this study is PFS rate at 16 weeks (CLL after BCR targeted therapy, MCL, and DLBCL) or 24 weeks (CLL and iNHL). PFS is defined as the interval from the first dose of ENTO to the earlier of the first documentation of definitive disease progression or death from any cause.

The determination of NHL response and progression (defined in the Protocol Section 6.20) is based on standardized criteria {Cheson 2007, Rourke 2010} as specifically modified for this study to reflect the biology of the diseases under study and the pharmacology of ENTO and the methods to be used in evaluation. The determination of CLL response and progression (defined in the Protocol Section 6.21) is based on standardized IWCLL criteria {Hallek 2008} as specifically modified for this study considering the pharmacology of ENTO and the methods to be used in evaluation.

In accordance with the Gilead Protocol 339-0102 Imaging Charter, if there is uncertainty regarding whether there is true progression, the subject may continue study treatment and remain under close observation (eg, evaluated at 4-week intervals). If subsequent evaluations suggest that the subject is experiencing progression, then the date of progression should be the time point at which progression was first identified. A single PD determination followed by a determination that indicated either no change or improvement in disease prior to the single PD observation will not be considered as PD.

Subjects without progression or death will be censored at the last adequate post-baseline tumor assessment time. If subjects receive other anti-cancer therapy or have  $\geq 2$  consecutive missing post-baseline tumor assessments immediately before documented progression or death, they will be censored at the last adequate post-baseline tumor assessment time before starting anti-cancer therapy or before  $\geq 2$  consecutive missing tumor assessments whichever is earlier. If subjects don't have adequate baseline tumor assessment or adequate post-baseline tumor assessment, they will be censored on the date of Study Day 1 unless subjects die before or on the 2nd scheduled post-baseline tumor assessment without receiving other anti-cancer therapy. Please see [Appendix 2](#) for details on PFS event and censoring time derivation.

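### The Protocol gives conflicting rules on whether LPL/WM subjects need progressive disease at entry, and the SAP pools them with SLL and MZL in the Week 24 PFS rate instead of reporting by histology

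*Protocol*

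**What the plan says.** The entry rule for LPL/WM appears in three places in the Protocol.

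- **Synopsis, inclusion criterion 3:** "Prior treatment for lymphoid malignancy and requiring treatment for progressive disease". It continues: "Criteria for progressive disease is established Cheson criteria for NHL and by IWCLL criteria for CLL, and for LPL/WM patients per Update on Recommendations", citing the Waldenström workshop. LPL/WM gets its own yardstick for progression and no exemption from it.
- **Section 4.1:** "selected types of B-cell NHL, with progressive disease are eligible for the study". iNHL is on the list that follows, with no LPL/WM exception.
- **Section 4.2.1, criterion 3a:** "LPL/WM patients do not need to have progressive disease but need to meet criteria of needing treatment". Here the same workshop reference defines need for treatment, not progression.

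Criterion 5a stands in both the Synopsis and Section 4.2.1: "Subjects with LPL/WM who do not have radiographically measurable progressive disease must have a monoclonal serum IgM" of at least twice the upper limit of normal, with marrow involvement.

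On analysis, the primary endpoint for iNHL is the Week 24 PFS rate by independent review (SAP 6.1.1 and 6.1.2). The Statistical Methods part of the Synopsis says iNHL data will be shown separately for FL, SLL, LPL and MZL. SAP Table 3-1 has a single Other iNHL column, and SAP 3.4 reads "No planned subset analyses". SAP 6.3, on changes from the protocol, mentions only the synoptic report and the dropped sensitivity analyses. SAP 4.3 summarises enrolled subjects who did not meet the eligibility criteria.

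**The concern.** The same LPL/WM subject can be eligible under one part of the Protocol and ineligible under another. That makes the SAP 4.3 count ambiguous.

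It also bears on the primary result. SLL and MZL subjects must be progressing at entry under every version of the rule, and LPL/WM subjects may not have been. In a single-arm cohort, where the outcome is being progression-free at a fixed time, disease course at entry cannot be separated from drug effect. If groups admitted under different rules are merged into one rate, a reader cannot tell what population it describes. The by-histology display that would let the reader see this has dropped out of the SAP without being declared.

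**Working it through.** **1. Apply each text to one hypothetical subject.** Take a previously treated LPL/WM subject who needs treatment, has IgM at least twice the upper limit of normal with marrow involvement, and has no documented progression.

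- Section 4.2.1: meets 3a and 5a, so eligible.
- Synopsis: meets 5a but fails criterion 3, so not eligible.
- Section 4.1: lacks progressive disease, so not eligible.

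Criterion 5a does not settle the matter. It waives only radiographically measurable progression, and what it asks for instead (an IgM level and marrow involvement) describes a state, not a change. In the SAP 4.3 table this subject counts as 0 or 1 depending on the text chosen. An SLL or MZL subject without progression fails under all three.

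**2. Cohort size.** Protocol Section 8.7 gives 45 for LPL, SLL and MZL together. This fits the stated total: maximum 4×40 + 45 + 3×60 = 385; minimum 4×10 + 45 + 2×20 + 60 = 185. Both reproduce. The split of the 45 by histology is not given.

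**3. Timing of progression calls.** Section 6.20.7.7 advises at least 4 months of treatment before progression is assessed in LPL/WM, absent compelling evidence. Four months is 4 × 365.25/12/7 ≈ 17.4 weeks, which leaves 24 − 17.4 = 6.6 weeks before the endpoint. Scheduled assessments fall at Weeks 8, 16 and 24 (Section 6.5), so only the last comes after that point. Section 6.5 also does not require repeat scans in LPL/WM subjects without lymphadenopathy at screening unless clinically indicated. On the other hand, Section 6.20.7.7 dates confirmed progression back to when it was first identified, so the net effect on the Week 24 rate is not determined.

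**4. Possible size, by assumption only.** If m of the 45 have a Week 24 rate differing by d from the rest, the pooled rate moves by m×d/45.

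- d = 0.4 (for example 0.8 against 0.4): m = 4, 8, 12 gives 3.6, 7.1, 10.7 points.
- d = 0.2 (for example 0.7 against 0.5): m = 4, 8, 12 gives 1.8, 3.6, 5.3 points.
- A negative d gives the same shifts downward.

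For scale, the binomial standard error at a rate of 0.4 is √(0.4×0.6/45) = 0.073, or 7.3 points. Five of the six shifts are smaller than that. Neither m nor d can be read from the documents.

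**5. Planned decisions.** Sections 1.6 and 3.1.3 exclude this cohort from the Bayesian futility review. The boundary and Table 8-3 do not apply to it.

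**6. Can progression at entry be recovered from screening?** IgM progression needs a rise of at least 25% from nadir and at least 0.5 g/dL, confirmed at least 6 weeks (42 days) apart (Section 6.20.7.7). Screening lasts at most 35 days, and Section 6.2.1 lists no collection of a prior nadir IgM. A progressing/not-progressing split could not be made reliably. Histology, and whether a subject had measurable disease on the screening scan, can be identified.

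**The case against.** The strongest reply is that the working rule is clear enough. The Synopsis refers to the Protocol for details, Section 4.1 speaks of subjects who meet the eligibility criteria, and Section 4.2 is the eligibility list, with 3a a specific exception inside it. Sites probably followed 4.2.1. That is plausible, but no text says so. Synopsis criterion 3 is not a general phrase that overlooked LPL/WM: it names that group and tells the reader how to judge its progression.

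The second reply is that little turns on it. The cohort is exploratory and descriptive, has no stopping rule, and any shift in the rate is assumed. This stands, and it limits the point to how the rate is interpreted.

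A reader might infer something stronger: that LPL/WM subjects who were not progressing would have stayed progression-free without the drug, so the Week 24 rate is inflated. Inputs can be chosen to make that look serious. With a rate of 0.10 in 35 subjects and 0.70 in 10, the pooled rate is (3.5 + 7)/45 = 0.233, above the 20% level that Section 1.6 calls not promising. The documents do not support the inference. Criterion 3a still requires need for treatment, so it does not admit quiescent patients. No passage gives an untreated Week 24 rate, the number of LPL/WM subjects, or how many were not progressing.

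**Conclusion.** The contradiction on LPL/WM entry is real, is in current text, and makes the SAP 4.3 count depend on an unstated choice. The pooled Other iNHL Week 24 PFS rate may combine subjects entered under different rules and assessed under different guidance on when to call progression. The size and direction of any effect cannot be determined. The 1.8 to 10.7 point range rests wholly on assumed numbers and rates, and inflation of the rate is not shown.

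Separately, and without any assumption, the SAP omits the by-histology presentation promised in the Synopsis and does not list the omission in 6.3. Restoring it addresses the comparability problem with data already held.

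**What to change.** 1. Reconcile Synopsis criterion 3, Section 4.1 and Section 4.2.1 criterion 3a so that they state one LPL/WM entry rule. Which rule is right is for the sponsor to say. Name in SAP 4.3 the text against which eligibility deviations are counted.
2. In SAP 3.2 (Table 3-1) and 6.1.2, report the Week 24 PFS rate with its 95% CI separately for LPL/WM, SLL and MZL, and give the pooled Other iNHL rate with and without LPL/WM.
3. Optionally, flag LPL/WM subjects admitted under criterion 5a rather than criterion 5, using the screening data.
4. If the by-histology presentation is to be dropped, list that in SAP 6.3 as a change from the protocol.

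The cost is wording plus a few table rows. The MM-formulation cohorts are closed to enrolment (footnote to Protocol Table 5-1), so the change that can still affect the reported result is in the analysis. The downside is wide intervals: if the 45 split evenly, 15 per histology at a rate of 0.4 gives a standard error of √(0.4×0.6/15) = 0.126, so an approximate 95% interval of ±25 points (1.96 × 0.126), against ±14 points (1.96 × 0.073) for the pooled cohort.
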